11.3 Dose Modifications for Hepatic Impairment

. For patients with mild liver impairment (Child-Pugh class A), the recommended dose is 140 mg daily (one capsule). Avoid the use of IMBRUVICA in patients with moderate or severe hepatic impairment (Child-Pugh classes B and C).

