	
Cohort B:
 
FL
 
 - Disease burden: lymph node size <5cm and/or extra-nodal involvement <5 cm 
AND
 
 -Relapsed/refractory FL ≥ 2 lines of therapy. Prior ibrutinib therapy is permitted 
HD
 
 - Disease burden: lymph node size <5cm and/or extra-nodal involvement <5 cm 
AND
 
 -Relapsed/refractory HD ≥ 2 lines of therapy 
 • Prior to administration of ibrutinib (day 60 to day 90 post HCT) 
 ○ KPS ≥ 60% ○ Engraftment of neutrophils (ANC ≥ 1.0 X10⁹/L) for 3 days without g-csf support ○ Platelets ≥100,000/mm³ or ≥50,000/mm³ if bone marrow involvement independent of transfusion support in either situation ○ GFR ≥ 30 ml/min ○ LFTs (ALT and AST) ≤ 3 X ULN; total bilirubin ≤ 1.5 mg/dL XULN unless bilirubin rise is due to Gilbert's syndrome or of non-hepatic origin ○ Predominant donor chimerisms of ≥ 51% as measured by CD3 and CD33 (or other myeloid marker)

Exclusion criteria
	
 • Pre-SCT 
 ○ Progression of CLL or MCL or FL or HD at time of transplant ○ Use of Coumadin (warfarin) or other vitamin-K antagonists for anticoagulation. Non-coumadin anticoagulation is permitted. ○ Active uncontrolled CNS involvement ○ Active uncontrolled bacterial or invasive fungal infections ○ History of malignancy other than the underlying disease unless treated with a curative intent and/or no evidence of disease for at least 3 y OR expected to be cured with SCT ○ Planned use of post-HCT cyclophosphamide for GVHD prophylaxis ○ Anticipated planned donor lymphocyte infusion in the first 3 months post-SCT ○ T cell depleted HCT ○ Umbilical cord HCT ○ History of stroke or intracranial hemorrhage within 6 months prior to enrollment. ○ Clinically significant cardiovascular disease such as uncontrolled or symptomatic arrhythmias, congestive heart failure, or myocardial infarction within 6 months of Screening, or any Class 3 (moderate) or Class 4 (severe) cardiac disease as defined by the New York Heart Association Functional Classification.

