10. ELIGIBILITY CRITERIA: EXCLUSION

Pre-SCT

1. Progression of CLL or MCL or FL or HD at time of transplant
2. Use of Coumadin (warfarin) or other vitamin-K antagonists for anticoagulation. Non-coumadin anticoagulation is permitted.
3. Known CNS involvement
4. Active uncontrolled bacterial or invasive fungal infections
5. History of malignancy other than the underlying disease unless treated with a curative intent and/or no evidence of disease for at least 3 y OR expected to be cured with SCT
6. Planned use of post-HCT cyclophosphamide for GVHD prophylaxis
7. Anticipated planned donor lymphocyte infusion in the first 3 months post-SCT
8. T deplete HCT
9. Umbilical cord HCT
10. History of stroke or intracranial hemorrhage within 6 months of enrollment.

11. Clinically significant cardiovascular disease such as uncontrolled or symptomatic arrhythmias, congestive heart failure, or myocardial infarction within 6 months of Screening, or any Class 3 (moderate) or Class 4 (severe) cardiac disease as defined by the New York Heart Association Functional Classification.
12. Known HIV
13. Active Hepatitis B or C virus
14. Child-Pugh Class C

Prior to Administration of Ibrutinib (Day 60-Day 90 Post SCT)

1. In the critical care unit, or use of mechanical ventilation or use of renal replacement therapy at any time post HCT and prior to administration of ibrutinib
2. Active uncontrolled stage 3-4 acute GI GVHD prior to administration of ibrutinib
3. Active uncontrolled stage 4 acute liver GVHD prior to administration of ibrutinib
4. Evidence of progressive disease as compared to pre-HCT (persistence of disease is permitted)
5. Anticipated planned donor lymphocyte infusion in the first 3 months post-SCT
6. Active uncontrolled bacterial or invasive fungal infections
7. Prednisone equivalent of >2mg/kg for treatment of GVHD prior to administration of ibrutinib
8. Use of second line systemic therapy for treatment of acute GVHD prior to administration of ibrutinib
9. Any life-threatening illness, medical condition, or organ system dysfunction which, in the investigator's opinion, could compromise the subject's safety, interfere with the absorption or metabolism of ibrutinib capsules, or put the study outcomes at undue risk including the presence of chronic/active HBV and HBC infections and Child-Pugh Class C.
10. Major surgery or a wound that has not fully healed within 4 weeks of starting ibrutinib

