 - Signed and completed Eligibility Checklist. **To be eligible for registration to the study, the participant must meet each inclusion and exclusion criterion listed in the eligibility checklist.**

Note: All study documents should be received 24-48 hours prior to the patient's anticipated start date. Same day treatment registrations will only be accepted with prior notice and discussion with the Coordinating Center. Please email the Coordinating Center if enrollment is needed sooner.

Upon satisfactory review of eligibility documents submitted, the Coordinating Center will approve enrollment and issue a subject ID number if one was not issued at screening. Once registration/enrollment confirmation from Coordinating Center is received, proceed with protocol procedures.

Please contact the assigned Study Contact with any questions regarding this process. You can also reach out to your assigned CRA once the study is activated.

The VICC Coordinating Center will assign Subject ID numbers to all patients whose eligibility has been confirmed. Only patients deemed eligible will be registered to investigational treatment.

Sequence/study ID numbers will not be re-used if a patient screen fails. Following registration, eligible participants should begin study treatment consistent with the protocol no later than [XXX days/weeks] after registration/enrollment by the VICC Coordinating Center. If a participant does not receive protocol therapy following registration within the allowed time period, the participant's registration on the study will be canceled. The Study Contact should be notified of cancellations as soon as possible. Patients being re-screened will need to consent to repeated procedures. As such, the Coordinating Center will require a new, signed Informed Consent document.

Issues that would cause treatment delays should be discussed with the Protocol Chair. Any requests for eligibility exceptions and/or deviations must be approved in writing by the Protocol Chair and the VICC DSMC.

As is generally accepted, standard of care procedures performed prior to consent, but within the protocol defined screening window for each assessment, can be used for study purposes. All research-only procedures must be performed after patient consent.

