20. STUDY SCHEDULE

Informed Consent

- The subject must read, understand, and sign the Institutional Review Board/Research Ethics Board/Independent Ethics Committee (IRB/IEC) approved informed consent form (ICF) confirming his or her willingness to participate in this study before any study-specific screening procedures are performed. Performance of procedures considered standard of care within window of screening but prior to consent will be permitted. Subjects must also grant permission to use protected health information per the Health Insurance Portability and Accountability Act (HIPAA).
- In addition, subjects must sign all approved ICF amendments per the site IRB/IEC guidelines during the course of the study.

Confirm Eligibility

- Eligibility will be confirmed pre-HCT and then second confirmation will be prior to administration of ibrutinib between day 60-90 post-HCT.
- Complete enrollment checklist and submit to coordinating center for review prior to enrollment. Preparative regimen for HCT should not be started until enrollment checklist has been reviewed and approved by coordinating center. A minimum of 48 hour notice will be mandated.

- Second confirmation: Complete enrollment checklist and submit to coordinating center for review and approval prior to start of ibrutinib between day 60-90 post-HCT. Ibrutinib will not be started until enrollment checklist has been reviewed and approved by coordinating center. A minimum of 48 hour notice will be mandated.

Pre-SCT: Screening visit:

All research studies to be completed within 4 weeks of starting preparative regimen unless specified otherwise. Timing of all pre-SCT standard of care assessments may be completed per the institutional practice.

- Standard of care: History and physical including Karnofsky performance status (KPS) (See the Clinical Assessment Manual)
- Standard of care: Transplant evaluation: follow institutional protocol on timing of evaluation prior to HCT and at a minimum will include:
 - Hematology
 - Hematology parameters performed at local laboratory will include a complete blood count: white blood cells, red blood cells, hemoglobin, hematocrit, platelets, and absolute neutrophil count.
 - Chemistry
 - Serum chemistry parameters performed at local laboratory will include: creatinine, AST, ALT, alkaline phosphatase, and total bilirubin.
 - Coagulation studies

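### The pre-ibrutinib exclusion names only Child-Pugh class C, although section 11.3 says to avoid the drug in class B as well

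*Combined protocol and SAP*

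**What the plan says.** Section 11.3 sets the hepatic rules for dosing. For the more severe classes it says "Avoid the use of IMBRUVICA in patients with moderate or severe hepatic impairment (Child-Pugh classes B and C"; for the mildest, "For patients with mild liver impairment (Child-Pugh class A), the recommended dose is 140 mg daily (one capsule".

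The eligibility text applied between day 60 and day 90, before ibrutinib starts, is narrower. Item 9 of that list in section 10, repeated in the synopsis, excludes serious illness or organ dysfunction that the investigator thinks could endanger the patient or "interfere with the absorption or metabolism of ibrutinib capsules". It ends with examples: "including the presence of chronic/active HBV and HBC infections and Child-Pugh Class C". The pre-transplant list in section 10 (item 14) also names only class C.

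Other liver-related criteria apply at the same time. The inclusion criteria require "LFTs (ALT and AST) ≤ 3 X ULN; total bilirubin ≤ 1.5 mg/dL XULN", with the bilirubin ceiling lifted where the rise comes from Gilbert's syndrome or from outside the liver. The exclusions include "Active uncontrolled stage 4 acute liver GVHD prior to administration of ibrutinib".

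The eligibility check controls release of the drug. Section 20 says "Ibrutinib will not be started until enrollment checklist has been reviewed and approved by coordinating center", and section 19 says "the participant must meet each inclusion and exclusion criterion listed in the eligibility checklist".

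**The concern.** The prohibition on class B stands only in a dose-modification subsection. The criteria that a site and the coordinating center confirm before the first dose name class C and go no further. Someone working from section 10 or the synopsis finds no line that stops a class B patient. Because class C is named by itself, that person may take class B to be acceptable.

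What is at stake is patient safety and the consistency of the protocol. A patient whom the dosing section says not to treat could be cleared to start at day 60-90. The efficacy analysis is not at issue.

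**Working it through.** No arithmetic applies to the main point. The check is a comparison of every place where hepatic function governs whether ibrutinib may be given.

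1. **Section 11.3:** classes B and C are both to be avoided.
2. **Synopsis, exclusions before ibrutinib:** class C is named; class B is not.
3. **Section 10, exclusions before ibrutinib, item 9:** same wording as the synopsis; class C only.
4. **Section 10, pre-transplant exclusions, item 14:** class C only. No ibrutinib is given at that stage, so this item does not control the first dose.
5. **Synopsis and section 9 item 11, laboratory limits before ibrutinib:** ALT, AST and bilirubin are capped, but no Child-Pugh class is stated. The documents do not link these limits to a class, so meeting them cannot be taken to rule out class B.
6. **Exclusions for liver GVHD and hepatitis:** these address particular causes of liver disease. They do not address the degree of impairment in general.
7. **The catch-all in item 9:** the list is open, and dysfunction affecting ibrutinib metabolism is expressly within it. An investigator may therefore exclude a class B patient. The wording leaves this to opinion and does not require it.

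Class B therefore appears in the dosing rule (1) and in none of the eligibility criteria (2 to 6). It can be reached only through judgment (7).

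A lesser point concerns class A. Section 11.2 raises the dose to 420 mg once azoles stop and does not mention section 11.3, which recommends 140 mg in mild impairment. The rule in 11.1 on stopping azoles is tied to patients whose 140 mg dose was due to the azole, so it does not plainly reach a patient who also has a hepatic reason for that dose. Section 11.3 already supplies the class A dose; what 11.2 lacks is a cross-reference.

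**The case against.** The strongest reply is that the protocol must be read as a whole. Section 11.3 is in force and says what to do about class B. An investigator who has read it has clear grounds under item 9 to exclude such a patient, and the laboratory, GVHD and hepatitis criteria narrow the gap further. On this view the omission is only one of drafting. Much of this stands: the practical risk is reduced, and a careful site would probably act correctly. The reply does not supply the missing criterion, and the criteria are what the coordinating center approves before the drug is started.

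Two stronger readings are tempting, and the documents support neither.

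- A reader might infer that the two sections contradict each other, one admitting class B patients and the other barring them. No criterion says a class B patient may be treated. The criteria are silent, and section 11.3 is the only text that speaks to class B. This is an omission.
- A reader might infer that class A patients will receive three times their intended dose (420 / 140 = 3) for most of the treatment period once the azole stops. That follows only if section 11.3 is ignored. Sections 11.2 and 11.3 are parallel rules with different triggers, and the end of azole use does not cancel the hepatic rule. The threefold dose is therefore not a consequence of following the plan. Nor does the 420 mg dose in section 6.5 and the synopsis schedule show otherwise: those places give starting doses and do not repeat the toxicity reductions of 11.1 either.

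**Conclusion.** The point holds as a mismatch. Section 11.3 says to avoid ibrutinib in classes B and C, while the exclusion confirmed before the first dose names class C alone, so no eligibility criterion expressly stops a class B patient. The mitigating text reduces the risk but does not remove the mismatch.

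The size cannot be stated. The documents give no Child-Pugh distribution at day 60-90, and the number of class B patients who would pass the laboratory limits is unknown. The sample size, power and primary analysis do not depend on this point. The eligibility checklist is not in the documents; if it already lists class B, the gap in practice is smaller, though the protocol text would still need aligning.

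The change should be made because it concerns safety and costs almost nothing. The class A matter is a minor clarification.

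**What to change.** - In the exclusion applied before ibrutinib, in both the synopsis and section 10 item 9, replace *Child-Pugh Class C* with *Child-Pugh Class B or C*.
- Make the same change in the pre-ibrutinib eligibility checklist if it lists only class C.
- Leave the pre-transplant exclusion as it is, since no ibrutinib is given then.
- Optional: in section 11.2, after the sentence that raises the dose to 420 mg, add *subject to 11.3 for patients with mild liver impairment*. Keeping the reference to mild impairment prevents the addition from being read more widely than section 11.3.

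The cost is a short wording change in two places, possibly a checklist edit, and one optional phrase. No new assessment is needed, because the existing class C exclusion already requires the class to be judged. The downside is that a few patients whom section 11.3 already says not to treat become ineligible to start ibrutinib.

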12. PROHIBITION AND RESTRICTIONS

The following guidance should be applied during the perioperative period for subjects who require surgical intervention or an invasive procedure while receiving ibrutinib:

- For any planned surgery or invasive procedure requiring sutures or staples for closure, ibrutinib should be held at least 7 days prior to the intervention and should be held at least 7 days after the procedure, and restarted at the discretion of the investigator when the surgical site is reasonably healed without serosanguineous drainage or the need for drainage tubes.

- For planned minor procedures (such as a central line placement, needle biopsy, thoracentesis, or paracentesis) ibrutinib should be held for at least 3 days prior to the procedure and should not be restarted for at least 3 days after the procedure. For bone marrow biopsies that are performed while the subject is on ibrutinib, it is not necessary to hold ibrutinib for these procedures.
- For emergency procedures, ibrutinib should be held after the procedure until the surgical site is reasonably healed, for at least 7 days after the urgent surgical procedure, or at the discretion of the investigator.

13. CONCOMITANT MEDICATIONS

13.1 Permitted Concomitant Medications

Supportive medications in accordance with standard practice (such as for emesis, diarrhea, etc.) are permitted. Use of neutrophil growth factors (filgrastim and pegfilgrastim or other biosimilar GCSF) or red blood cell growth factors (erythropoietin) is permitted per institutional policy and in accordance with the ASCO guidelines. Transfusions may be given in accordance with institutional policy.

13.2 Medications to be Used with Caution

CYP3A Inhibitors/Inducers

Concomitant use of ibrutinib and drugs that strongly or moderately inhibit CYP3A can increase ibrutinib exposure, and strong CYP3A inhibitors should be avoided. In healthy volunteers, co-administration of ketoconazole, a strong CYP3A inhibitor, increased C_{max} and AUC of ibrutinib by 29- and 24-fold, respectively.

Voriconazole and posaconazole can be used concomitantly with ibrutinib, with dose modifications as described above in Section 11.2.

Strong inhibitors of CYP3A (eg, ketoconazole, indinavir, nelfinavir, ritonavir, saquinavir, clarithromycin, telithromycin, itraconazole, nefazodone, and cobicistat) should be avoided, and an alternative with less CYP3A inhibitory potential should be considered.

For strong CYP3A inhibitors used short-term (e.g., antifungals and antibiotics for 7 days or less, e.g., ketoconazole, itraconazole, voriconazole, posaconazole, clarithromycin, telithromycin) consider interrupting IMBRUVICA therapy during the duration of inhibitor use.

Concomitant use of strong CYP3A inhibitors which would be taken chronically (e.g., ritonavir, indinavir, nelfinavir, saquinavir, boceprevir, telaprevir, nefazodone) is not recommended.

Patients taking concomitant strong or moderate CYP3A4 inhibitors should be monitored more closely for signs of IMBRUVICA toxicity. Avoid grapefruit and Seville oranges during IMBRUVICA treatment, as these contain moderate inhibitors of CYP3A.

Administration of ibrutinib with strong inducers of CYP3A decreases ibrutinib plasma concentrations by up to 90%. Avoid concomitant use of strong CYP3A inducers (e.g., carbamazepine, rifampin, phenytoin and St. John's Wort). Consider alternative agents with less CYP3A induction.

A comprehensive list of inhibitors, inducers, and substrates may be found at <http://medicine.iupui.edu/clinpharm/ddis/table.aspx>. This website is continually revised and should be checked frequently for updates.

13.3 Drugs That May Have Their Plasma Levels Altered by Ibrutinib

In vitro studies indicated that ibrutinib is a weak reversible inhibitor toward CYP2B6, CYP2C8, CYP2C9, CYP2C19, CYP2D6, and CYP3A4/5 and does not display time-dependent CYP inhibition. The dihydrodiol metabolite of ibrutinib is a weak inhibitor toward CYP2B6, CYP2C8, CYP2C9, and CYP2D6. Both ibrutinib and the dihydrodiol metabolite are at most weak inducers of CYP450 isoenzymes in vitro. Therefore, it is unlikely that ibrutinib has any clinically relevant drug-drug interactions with drugs that may be metabolized by the CYP450 enzymes.

In vitro studies indicated that ibrutinib is not a substrate of P-glycoprotein (P-gp), but is a mild inhibitor (with an IC₅₀ of 2.15 µg/mL). Ibrutinib is not expected to have systemic drug-drug interactions with P-gp substrates. However, it cannot be excluded that ibrutinib could inhibit intestinal P-gp after a therapeutic dose. There is no clinical data available. Therefore, to avoid a potential interaction in the GI tract, narrow therapeutic range P-gp substrates such as digoxin, should be taken at least 6 hours before or after ibrutinib.

13.4 Antiplatelets and Anticoagulants

Fatal bleeding events have occurred in patients treated with IMBRUVICA including grade 3 or higher bleeding events (subdural hematoma, gastrointestinal bleeding, hematuria and post procedural hemorrhage). IMBRUVICA may increase the risk of hemorrhage in patients receiving antiplatelet or anticoagulant therapies.

Consider the benefit-risk of withholding IMBRUVICA for at least 3 to 7 days pre and post-surgery depending upon the type of surgery and the risk of bleeding.

Warfarin or vitamin K antagonists should not be administered concomitantly with ibrutinib. Supplements such as fish oil and vitamin E preparations should be avoided. Use ibrutinib with caution in subjects requiring other anticoagulants or medications that inhibit platelet function. Subjects with congenital bleeding diathesis have not been studied. Ibrutinib should be held at least 3 to 7 days pre- and post-surgery depending upon the type of surgery and the risk of bleeding (refer to the Concomitant Medications section).

Subjects requiring the initiation of therapeutic anticoagulation therapy (other than warfarin or a vitamin K antagonist) during the course of the study should have treatment with ibrutinib held, and ibrutinib should not be restarted until the subject is clinically stable. Subjects should be observed closely for signs and symptoms of bleeding. No dose reduction is required when study drug is restarted.

13.5 Prohibited Concomitant Medications

Any chemotherapy, anticancer immunotherapy, experimental therapy, or radiotherapy is prohibited while the subject is receiving ibrutinib treatment. Localized, hormonal, or bone sparing treatment for non-B-cell malignancies may be considered with approval of the PI.

Warfarin or vitamin K antagonists should not be administered concomitantly with ibrutinib.

14. MANAGEMENT OF IMMUNOSUPPRESSION

Participants may be receiving other immunosuppressive therapies (including extra-corporeal photopheresis [ECP]) in addition to glucocorticoids. In addition, due to potential drug-drug interactions with ibrutinib, drug levels for immunosuppressant agents such as cyclosporine, tacrolimus, and/or sirolimus are highly recommended during the clinical trial. The doses for these immune-suppressants should be adjusted per institutional practices based on the measured drug level.

Other strategies of GVHD therapy including PUVA, UVB light therapy, topical use of calcineurin inhibitors (e.g. for ocular GVHD) is permitted.

